13.1 Trial Management Group (TMG)

The TMG will include the Chief Investigator and trial staff. The TMG will be responsible for overseeing the trial. The group will meet regularly, once per week at each site and will send updates to PIs.

The TMG will review recruitment figures, SAEs and substantial amendments to the protocol prior to submission to the REC. All PIs will be kept informed of substantial amendments through their nominated responsible individual.

13.2 Other committees

The role of the TSC is to provide overall supervision of the trial. The TSC will review the data, adverse events and any other issues identified and recommend any appropriate amendments/actions for the study as necessary. The TSC acts on behalf of the funder and Sponsor.

14. Ethical requirements and patient and public involvement

Ethics

The sponsor will ensure that the trial protocol, participant information sheet, consent form, GP letter and submitted supporting documents have been approved by the appropriate research ethics committee, prior to any participant recruitment. The protocol, all other supporting documents including and agreed amendments, will be documented and submitted for ethical and regulatory approval as required. Amendments will not be implemented prior to receipt of the required approval(s).

Before any NHS site may be opened to recruit participants, the Chief Investigator/Principal Investigator or designee must receive confirmation of capacity and capability in writing from the Trust Research & Development (R&D). It is the responsibility of the CI/ PI or designee at each site to ensure that all subsequent amendments gain the necessary approvals, including confirmation of capacity and capability at the site. This does not affect the individual clinician's responsibility to take immediate action if thought necessary to protect the health and interest of individual participants (see section 9.6 for reporting urgent safety measures).

An annual progress report (APR) will be submitted to the REC within 30 days of the anniversary date on which the favorable opinion was given, and annually until the trial is declared ended. The chief investigator will prepare the APR.

Within 90 days after the end of the trial, the CI/Sponsor will ensure that the main REC is notified that the trial has finished. If the trial is terminated prematurely, those reports will be made within 15 days after the end of the trial.

The CI will supply the Sponsor with a summary report of the trial, which will then be submitted to the REC within 1 year after the end of the trial.

Patient and public involvement (PPI)

The study recognises the importance of patient involvement in. A patient survey in outpatient clinic was performed. The survey asked the following questions:

- □ How does FI Impact your life?
- □ Do you therein there is a role for further investigating FI?
- □ Would additional testing at a routine appointment be an acceptable method for the study?
- □ If a study was recruiting would you participate?

The patient response was positive, with all those surveyed expressing need for investigation and willingness to participate. The method was also identified as acceptable.

15. Monitoring

The sponsor has determined the study to be low risk and has advised the following monitoring process:

Each site to e-mail the sponsor annually:

- Delegation log
- Adverse event log
- Deviation log
- Minutes of Trial Steering Committee
- Annual progress report (Lead site only) when sent to Ethics Committee

16. Finance

The study has been funded by the GI Physiology Unit at UCLH. 2 MAPLe devices have been purchased by the departmental charity. Ongoing funding has been agreed by each trust for the purchasing of probes to be used within each trust. There are no financial interests in they study.

17. Insurance

University College London holds insurance against claims from participants for injury caused by their participation in the trial. Participants may be able to claim compensation if they can prove that UCL has been negligent. However, as this trial is being carried out in a hospital, the hospital continues to have a duty of care to the participant of the trial. University College London does not accept liability

for any breach in the hospital's duty of care, or any negligence on the part of hospital employees. This applies whether the hospital is an NHS Trust or otherwise.

Participants may also be able to claim compensation for injury caused by participation in this trial without the need to prove negligence on the part of University College London or another party. Participants who sustain injury and wish to make a claim for compensation should do so in writing in the first instance to the Chief Investigator, who will pass the claim to the Sponsor's Insurers, via the Sponsor's office.

Hospitals selected to participate in this trial shall provide negligence insurance cover for harm caused by their employees and a copy of the relevant insurance policy or summary shall be provided to University College London, upon request.

The MAPLe is covered by a 3 year indemnity. Should the device break or malfunction it will be returned to the manufacturer for repairs and a replacement provided. Should the original device be irreparable it will be replaced free of charge.

18. Intellectual property

All background intellectual property rights (including licenses) and know-how used in connection with the study shall remain the property of the party introducing the same and the exercise of such rights for purposes of the study shall not infringe any third party's rights.

All intellectual property rights and know-how in the protocol and in the results arising directly from the study, but excluding all improvements thereto or clinical procedures developed or used by each participating site, shall belong to UCLH. Each participating site agrees that by giving approval to conduct the study at its respective site, it is also agreeing to effectively assign all such intellectual property rights ("IPR") to UCL and to disclose all such know-how to UCL.

Each participating site agrees to, at the request and expense of UCL execute all such documents and do all acts necessary to fully vest the IPR in UCL.

Nothing in this section shall be construed so as to prevent or hinder the participating site from using know-how gained during the performance of the study in the furtherance of its normal activities of providing or commissioning clinical services, teaching and research to the extent that such use does not result in the disclosure or misuse of confidential information or the infringement of an intellectual property right of UCL. This does not permit the disclosure of any of the results of the study, all of which remain confidential.

19 Appendices

Appendix 1 - Schedule of assessments

	Screening (Pre- treatment assessment)	Intervention phase		Final visit	
Visit No:	1	2	3	4	
	Day – X to Day -X	Day 1	Day 7	6 Months	
Window of flexibility for timing of visits:			+/- 7 Days	+/- 14 days	
Informed Consent		Х			
Medical History	Х				
Physical Examination					
Eligibility confirmation	Х	Х			
Faecal incontinence Questionnaire		Х			
Quality of Life Questionnaire	Х				
Anal Ultrasound	UCLH X	ASPH X			
Prescribed History		Х			
HRAM		Х			
MAPLe		Х		If treatment advised x	
MDT			Х		
Adverse Events review	Х	Х	Х	Х	
Concomitant Medication review (if applicable)	Х	Х			

Appendix 2 - CE Certificate

Please see attached PDF

Appendix 3 - St Mark's Incontinence Score

St Mark's Incontinence Score

	Never	Rarely	Sometimes	Weekly	Daily
Incontinence for solid stool	0	1	2	3	4
Incontinence for liquid stool	0	1	2	3	4
Incontinence for gas	0	1	2	3	4
Alteration in lifestyle	0	1	2	3	4
		Yes		No	
Need to wear pad or plug			0		2
Taking constipating medications		0)	
Lack of ability to defer defacation for 15 mins			0		4

Definitions

Never: No episodes in the past 4 weeks

Rarely: One episode in the past 4 weeks

Sometimes: More than one episode in the past 4 weeks but less than once per week

Weekly: One or more episodes per week but less than one per day

Daily: One or more episodes per day

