The role of sEMG in clinical assessment of FI has been limited to research and has not been correlated with current gold standard techniques. This study aims to investigate the sEMG of symptomatic patients using MAPLe. The study will test the non-inferiority of MAPLe against HRAM and AUS in assessing FI. Non-inferiority of a test is defined as the test being no worse than the competitor. The study will aim to identify if particular patient groups have closer correlation

between symptom profiles and FI scores and sEMG results, and whether sEMG improves following treatment. The study will endeavor to identify the clinical utilisation of sEMG in FI.

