3.1 Assessment and Management of Risk

The table below summarise the risks and mitigations of all test above standard care that are being performed in a table:

Intervention	Potential risk	Risk Management
Assessment with MAPLe device	The device will be placed anally and record sEMG, not providing stimulation. As the device will be used in the same nature as current assessment devices no additional risk is perceived.	Performed by trained operator.

4. Objectives

Primary: To determine the role of MAPLe in the assessment of FI in defined patient groups.

Secondary: To determine if targeted treatment is achieved following assessment with MAPLe.

5. Trial design

This is cohort study of participants with symptoms of faecal incontinence. It will take place across two hospital trusts, both able to provide specialist pelvic floor services and facilities required to meet the needs of the study and follow up required by the participants. The use of two sites aims to increase the yield and diversity of participants. The sample size for the study is 120 participants.

Following a stringent selection and recruitment process, participants will be invited to a designated ARP session where they will be consented, complete an incontinence and quality of life questionnaire, and undergo ARP assessment. This will comprise of the current gold standard, AUS and HRAM, and additional assessment with MAPLe using a standardised protocol. Through undertaking all three tests participants will act at their own controls. Participant participation will conclude following ARP assessment unless treatment is deemed necessary by their local MDT. These participants will be followed up at 6 months with interval MAPLe assessment and incontinence and quality of life questionnaire.

The results will undergo statistical analysis to determine non-inferiority of MAPLe in assessing FI. For analysis participants will be allocated to the following groups: fistula/chronic perianal conditions, obstetric injury <12 months, obstetric injury >12months, neurogenic. Each group will be analysed using symptoms profile and MAPLe results to identify correlation. Comparison of MAPle results pre and post treatment will determine if targeted treatment has been achieved.

An expert panel of pelvic floor specialists will be formed to determine the additional benefit of MAPLe in a clinical context. The panel will consist of 3-6 specialists within the field. To reduce bias,

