10.4 Data handling

The study is compliant with the requirements of General Data Protection Regulation (2016/679) and the Data Protection Act (2018). All investigators and study site staff will comply with the requirements of the General Data Protection Regulation (2016/679) with regards to the collection, storage, processing and disclosure of personal information, and will uphold the Act's core principles. UCL is the data controller; the UCL Data Protection Officer is [name] [contact]. The data processors are the Student Researcher and the Chief Investigator. The study will be collecting the following data: Age, gender, parity, medical and surgical history, drug history.

Once a participant is enrolled, they will be allocated an individual study number. No record of name/date of birth/address/telephone number will be made. A list of individual study number and associated hospital numbers will be recorded in an encrypted database on a computer within each trust. The list will only comprise of participants recruited from that trust. Data will be provided directly by the participants and recorded on a CRF by the student investigator. Investigation results will be recorded on the CRF. The CRF will not record personal data. The CRF and completed questionnaires will be stored in a locked filing cabinet in the GI physiology department at each trust only accessible to study personnel. The anonymised research data will be collated by the student researcher in an encrypted database on each trust computer. For analysis, a copy of the research data obtained at ASPH will be made and placed on an encrypted USB. This will be transferred to UCLH and combined with the research data from this site. This will be undertaken by the student researcher. The CRF and associated documents will be destroyed 2 years following completion of study by their trust. The electronic database will be stored for 5 years.

11. Statistical Considerations

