11.2 Secondary outcome(s)

The secondary outcome is to determine if following assessment with MAPLe targeted treatment is achieved. This will be defined by improvement in physiological assessment with MAPLe and incontinence questionnaires. This will be measured at 6 months following the end of recruitment at the end of study.

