11.5.2 Secondary outcome analysis

To determine if targeted treatment has been achieved participants will be grouped according to the treatment received: biofeedback, neuromodulation, rectal irrigation, and surgery.

Statistical comparison between MAPLe results pre and post treatment for each participant per group will be performed and analysed.

12. Record keeping and archiving

At the end of the trial, all essential documentation will be archived securely by the CI for a minimum of 20 years from the declaration of end of trial.

Essential documents are those which enable both the conduct of the trial and the quality of the data produced to be evaluated and show whether the site complied with all applicable regulatory requirements.

The sponsor will notify sites when trial documentation can be archived. All archived documents must continue to be available for inspection by appropriate authorities upon request.

13. Oversight Committees

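### Appendix 3, read in printed order, scores two St Mark's yes/no items in the opposite direction to the frequency items, and no rule in the plan corrects this (original page to be checked)

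*Combined protocol and SAP*

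**What the plan says.** Appendix 3 (St Mark's Incontinence Score) has two blocks. The first has four items (solid stool, liquid stool, gas, lifestyle), each scored 0 for never, 1 rarely, 2 sometimes, 3 weekly and 4 daily. The definitions below the table equate never with no episodes in four weeks, so 0 is the good end.

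The second block has the column headings Yes and No, in that order. "Need to wear pad or plug" carries 0 then 2, and "Lack of ability to defer defacation for 15 mins" carries 0 then 4. The row on constipating medication shows a 0, and its second value cannot be read. The appendix gives no total, maximum, direction or reverse-coding rule. The only reverse-coding instruction in the document is for Question 1 of the quality of life scale in Appendix 4.

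On how the score is used:

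- Section 11.2 says of the secondary outcome: "This will be defined by improvement in physiological assessment with MAPLe and incontinence questionnaires".
- Section 5 (Trial design) says of treated participants: "These participants will be followed up at 6 months with interval MAPLe assessment and incontinence and quality of life questionnaire".
- The rationale in Section 3 wants to know whether some patient groups show closer correlation "between symptom profiles and FI scores and sEMG results, and whether sEMG improves following treatment".
- Section 11.5.2 names only MAPLe for the before-and-after analysis: "Statistical comparison between MAPLe results pre and post treatment for each participant per group will be performed and analysed".
- Appendix 1 marks the row "Faecal incontinence Questionnaire" on Day 1 only.
- Section 10.4 provides that "The CRF and completed questionnaires will be stored in a locked filing cabinet".

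**The concern.** Both legible yes/no items are worded as problems, so a Yes answer means that the problem is present. Taken in printed order, the key rewards the problem with 0 and charges 2 or 4 points for its absence. The frequency items run the other way. A total that adds the two blocks would mix opposite directions.

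Two uses of the score would be exposed. The first is any analysis relating incontinence scores at a single visit to sEMG: the yes/no items would pull the total the wrong way and weaken or distort the association. The second is any change score at 6 months: a patient who no longer needs a pad, or who regains the ability to defer, would gain points instead of losing them. Real improvement could then read as no change or as worsening, in exactly the patients whose yes/no problems resolve.

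**Working it through.** The plan states no total, range or change score, so there is no figure to reproduce. The check uses the item values in Appendix 3 only and leaves out the medication row, so all totals below are six-item totals.

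**Inputs.** F = sum of the four frequency items, 0 to 4 × 4 = 16. P = 1 if a pad or plug is needed, otherwise 0 (weight 2). D = 1 if the patient cannot defer, otherwise 0 (weight 4).

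**Totals.**

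- In the same direction as the frequency items: F + 2P + 4D.
- As printed: F + 2(1 - P) + 4(1 - D) = F + 6 - 2P - 4D.
- Printed minus consistent: 6 - 4P - 8D.

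**Error at a single visit.**

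| Problem present | P, D | 6 - 4P - 8D |
|---|---|---|
| Neither | 0, 0 | +6 |
| Pad only | 1, 0 | +2 |
| Deferral only | 0, 1 | -2 |
| Both | 1, 1 | -6 |

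The worst six-item patient scores 16 + 2 + 4 = 22 on consistent scoring and 16 as printed. A symptom-free patient scores 0 and 6 respectively. Ranking can also reverse. With F = 8 for both, a patient with both problems and one with neither score 14 and 8 on consistent scoring, but 8 and 14 as printed. For such a pair the order is wrong whenever their frequency totals differ by less than 6.

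**Error in a change score (after minus before).** F cancels, leaving -4 × (change in P) - 8 × (change in D).

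| What resolves | Consistent change from these items | Printed change from these items | Shift |
|---|---|---|---|
| Neither answer changes | 0 | 0 | 0 |
| Pad | -2 | +2 | +4 |
| Deferral | -4 | +4 | +8 |
| Both | -6 | +6 | +12 |

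The signs reverse if a problem newly appears. For example, if F falls from 10 to 4 and both problems resolve, the consistent total goes from 16 to 4 (a fall of 12) and the printed total from 10 to 10 (no change). If F falls from 10 to 4 and both problems persist, the change is -6 either way (16 to 10 consistent, 10 to 4 printed).

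**The case against.** The strongest objection is that the evidence is one visibly damaged table. The values in the two legible rows sit one column to the right of the headings, and the medication row breaks differently. A uniform shift would keep left-to-right order, and both legible rows agree, so the reversed reading is the most natural one. But misplaced headings or cells cannot be excluded from the text alone. This objection stands to the extent that the page must be checked before anything is changed.

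Second, nothing shows that the printed values will be used. No section says how totals are formed or which values the CRF or database holds. This stands too. A reader might infer that all St Mark's totals in this study are wrong; the documents support that only if the printed values are both real and applied.

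Third, a reader might infer that the secondary outcome analysis is corrupted by up to 12 points. The documents do not go that far. Sections 5 and 11.2 call for a repeated questionnaire, but Section 11.5.2 compares only MAPLe results and Appendix 1 schedules the incontinence questionnaire on Day 1 only. The change score has a role in the outcome definition but no specified analysis. Likewise, the link between incontinence scores and sEMG is stated in the rationale; Sections 11.1 and 11.5.1 speak of symptom profile, correlation and regression without naming this total.

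What does not fall is the absence of any scoring rule that would override the printed key.

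**Conclusion.** The point holds conditionally, with medium confidence. As it reads, Appendix 3 reverses the pad or plug and deferral items relative to the frequency items, and the plan contains nothing that corrects this. If the order is confirmed on the page and the printed values are used, six-item totals are off by between -6 and +6 points at a single visit, and change scores by 4, 8 or 12 points when the pad problem, the deferral problem or both resolve. How many patients would be affected depends on how many change these answers, which the documents do not give.

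Nothing is claimed about the medication row, and 22 is not the maximum of the full scale. The error is recoverable because the completed questionnaires are kept, so it should be fixed but does not undermine the study.

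A smaller point needs the same page check. The Appendix 4 scoring key lists Q3d in both Scale 2 and Scale 3 and Q3c in neither. A reader might infer that Q3c belongs in Scale 2, but the appendix does not say so, and a misread letter is possible.

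**What to change.** 1. Check Appendix 3 on the original page, and check which values the CRF and database use.
2. If the printed order is confirmed, swap the two headings, so that pad or plug scores Yes 2 / No 0 and lack of ability to defer scores Yes 4 / No 0. Check the medication row and correct it only if it is also reversed.
3. State in the appendix that a higher total is worse, and give the maximum.
4. Compute totals, and re-score any already computed, from the answers on the stored questionnaires rather than from recorded totals.
5. Reconcile Sections 5 and 11.2 with Section 11.5.2 and Appendix 1 on whether the incontinence questionnaire is repeated at 6 months and, if so, how it is analysed.
6. On the original page of Appendix 4, check why Q3d appears twice and Q3c not at all.

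The scoring correction costs a page check, a corrected appendix page and a small change to the scoring code. It needs no new data or visits. Section 10.4 has the CRF and associated documents destroyed two years after study completion, so any re-scoring should be done before then.

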Appendix 4 - Quality of Life Questionnaire

Quality of life Questionnaire

Q 1: In general, would you say your health is:

- 1 [] Excellent
- 2 [] Very Good
- 3 [] Good
- 4 [] Fair
- 5 [] Poor

Q2: For each of the items, please indicate how much of the time the issue is a concern for you due to accidental bowel leakage. (If it is a concern for you for reasons other than accidental bowel leakage then check the box under Not Apply, (N/A).)

Due to accidental bowel leakage	Most of the Time	Some of the Time	A little of the time	None of the Time	N/A
I am afraid to go out	1	2	3	4	
I avoid visiting friends	1	2	3	4	
I avoid staying overnight away from home	1	2	3	4	
It is difficult for me to get out and do things like going to a movie or to church	1	2	3	4	
I cut down on how much I eat before I go out	1	2	3	4	
Whenever I am away from home, I try to stay near a restroom as much as possible		2	3	4	
near a restroom as much as possible	1	2	3	4	
It is important to plan my schedule around my bowel pattern	1	2	3	4	
I avoid traveling	1	2	3	4	
I worry about not being able to get to the toilet in time	1	2	3	4	
I feel I have no control over my bowels	1	2	3	4	
I can't hold my bowel movement long enough to get to the bathroom	1	2	3	4	
I leak stool without even knowing it	1	2	3	4	
I try to prevent bowel accidents by staying very near a bathroom	1	2	3	4	

Q3: Due to accidental bowel leakage, indicate the extent to which you AGREE or DISAGREE with each of the following items. (If it is a concern for you for reasons other than accidental bowel leakage then check the box under Not Apply, N/A).

Due to accidental bowel leakage:	Strongly Agree	Somewhat Agreee	Somewhat Disagree	Strongly Disagree	N/A
I feel ashamed	1	2	3	4	
I an not do many of things I want to do	1	2	3	4	
I worry about bowel accidents	1	2	3	4	
I feel depressed	1	2	3	4	
worry about others smelling stool on me	1	2	3	4	
I feel like I am not a healthy person	1	2	3	4	
I enjoy life less	1	2	3	4	
I have sex less often than I would like to	1	2	3	4	
I feel different from other people	1	2	3	4	
The possibility of bowel accidents is always on my mind	1	2	3	4	
I am afraid to have sex	1	2	3	4	
I avoid traveling by plane or train	1	2	3	4	
I avoid going out to eat	1	2	3	4	
Whenever I go someplace new, I specifically local where the bathrooms are.	/ 1	2	3	4	

Q 4: During the past month, have you felt so sad, discouraged, hopeless, or had so many problems that you wondered if anything was worthwhile?

- 1 [] Extremely So To the point that I have just about given up
- 2 [] Very Much So
- 3 [] Quite a Bit
- 4 [] Some Enough to bother me
- 5 [] A Little Bit
- 6 [] Not At All

Scales range from 1 to 5, with a 1 indicating a lower functional status of quality of life. Scale scores are the average (mean) response to all items in the scale (e.g., add the responses to all questions in a scale together and then divide by the number of items in the scale. Not Apply is coded as a missing value in the analysis for all questions.)

Scale 1. Lifestyle, ten items: Q2a Q2b Q2c Q2d Q2e Q2g Q2h Q3b Q31 Q3m

Scale 2. Coping/Behaviour, nine items: Q2f Q2i Q2j Q2k Q2m Q3d Q3h Q3j Q3n

Scale 3. Depression/Self Perception, seven items: Q1 Q3d Q3f Q3g Q3i Q3k Q4, (Question 1 is reverse coded.)

Scale 4. Embarrassment, three items: Q21 Q3a Q3e

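### The quality of life scoring key counts Q3d in two scales and Q3c in none, so the Coping score is miskeyed by up to 0.33 points; the stated 1 to 5 range is also unattainable

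*Combined protocol and SAP*

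**What the plan says.** The Quality of Life Questionnaire is the first of two appendices numbered 4. The form has a general health question (Q1, five options), a block of statements under Q2, a second block under Q3 (both with answers 1 to 4 or not applicable), and a closing question (Q4, six options). The key then assigns items to four scales. The entry for coping reads "Scale 2. Coping/Behaviour, nine items: Q2f Q2i Q2j Q2k Q2m Q3d Q3h Q3j Q3n". The entry for depression, where Q3d turns up a second time, reads "Scale 3. Depression/Self Perception, seven items: Q1 Q3d Q3f Q3g Q3i Q3k Q4, (Question 1 is reverse coded". Neither of the two remaining lists contains Q3c or Q3d: the lifestyle entry is "Scale 1. Lifestyle, ten items: Q2a Q2b Q2c Q2d Q2e Q2g Q2h Q3b Q31 Q3m", and the shortest list, for embarrassment, is "Scale 4. Embarrassment, three items: Q21 Q3a Q3e".

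A scale score is the mean response over the scale's items. The appendix illustrates this by telling the analyst to add the responses and "divide by the number of items in the scale. Not Apply is coded as a missing value in the analysis for all questions". On the possible values it says "Scales range from 1 to 5", with 1 the poorer end.

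Section 8.3 has participants complete the questionnaire at the anorectal physiology session. Section 5 repeats it at 6 months in those who are treated.

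**The concern.** A key that divides a form into separate scales should normally use each item once. Here Q3d contributes to two scales and one collected answer is never used. The misplaced item also changes content: Coping/Behaviour gains a statement about mood, which already belongs to Depression/Self Perception, and the statement about worrying over accidents, "I worry about bowel accidents", is dropped. At stake are a Coping score that is not the intended one and a built-in overlap between two scales meant to describe different things. Anyone comparing the scores with other work using the same instrument would not be comparing like with like.

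The stated range is a separate fault. It alters no computed score, but it misdescribes the scale on which differences would be judged and would mislead anyone using it as a range check on the data.

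**Working it through.** **Inputs.** The form and the key, both in the Quality of Life Questionnaire appendix. The rows carry no printed letters in the available text, so they are lettered in printed order. One Q2 statement, about staying near a restroom, is split over two lines and is treated as one row. The key prints Q21 and Q31; these are read as Q2l and Q3l and not counted as errors.

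**Step 1: reproduce the stated sizes.**
- Items on the form: 1 (Q1) + 13 (Q2a to Q2m) + 14 (Q3a to Q3n) + 1 (Q4) = 29.
- Entries in the key: 10 + 9 + 7 + 3 = 29. Each list has the length stated for it.

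**Step 2: count each item across the four lists.**
- Q1 and Q4: once each, both in Scale 3.
- Q2: a, b, c, d, e, g, h (Scale 1); f, i, j, k, m (Scale 2); l (Scale 4). All 13 letters once.
- Q3: b, l, m (Scale 1); d, h, j, n (Scale 2); d, f, g, i, k (Scale 3); a, e (Scale 4). The letter d occurs twice and c never; the other 12 occur once.
- Used once: 2 + 13 + 12 = 27. Adding the two uses of Q3d gives 29 entries, of which 28 are distinct.

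**Step 3: identify the two items.** In printed order the third Q3 statement is "I worry about bowel accidents" and the fourth is the one about feeling depressed. The fourth fits Scale 3 by content and the third fits Scale 2. Putting Q3c in place of Q3d in Scale 2 makes every item appear once and leaves the scale at nine items.

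**Step 4: size of the effect on Scale 2, all nine items answered.** Let S be the sum of the other eight answers.
- As written: (S + Q3d)/9. With Q3c: (S + Q3c)/9. Difference: (Q3c - Q3d)/9.
- Answers equal: 0. One category apart: 1/9 = 0.11. Two apart: 2/9 = 0.22. Opposite extremes: 3/9 = 0.33.

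**Step 5: attainable range.**
- Scales 1, 2 and 4 contain only items scored 1 to 4, so their means run from 1 to 4.
- Scale 3 contains Q1 (maximum 5 after reversal), Q4 (maximum 6) and five items with maximum 4. Its maximum is (5 + 6 + 5 x 4)/7 = 31/7 = 4.43.
- No scale can reach 5.

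**The case against.** **The text may be a misreading of the PDF.** The available text has no row letters, a split row and two letters rendered as the digit 1. A c read as d cannot be ruled out from this text alone. But the duplication and the gap are visible in the key's own letters, whatever the row order. The row lettering also fits the key elsewhere: its last letters, m and n, match 13 and 14 rows, and Q3a and Q3e fall on statements about shame and smell, as an embarrassment scale should. What stands is that the key must be checked against the source before it is changed.

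**The effect is small and confined.** This stands. One item in nine is affected, the 0.33 needs opposite extreme answers to two negatively worded statements, and the other three item lists are sound.

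**Little depends on it.** This also largely stands. Sections 11.1 and 11.2 do not name quality of life, and nor do the analyses in 11.5.1 and 11.5.2. A reader might infer that these scores belong to the symptom profile to be correlated with MAPLe, but the protocol never defines that term as including them. The Appendix 1 schedule, as it reads in the available text, marks the questionnaire only at screening, whereas Section 5 repeats it at 6 months.

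**The treatment of not-applicable answers.** A reader might also infer that the full item count is always the divisor, so that each such answer counts as zero and lowers the score. The documents do not support that. The divisor is given as an illustration of a mean, and the same parenthesis codes these answers as missing; a mean with missing values ordinarily uses the items answered. The full-divisor reading would also allow impossible scores: two answers of 1 and one not applicable on Scale 4 would give 2/3 = 0.67, below the stated minimum of 1. What remains is that the divisor and any minimum number of answers are left unstated.

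**Conclusion.** The point holds for one scale and for the range statement. As printed, the key uses Q3d twice and Q3c not at all, which makes the Coping/Behaviour score differ by (Q3c - Q3d)/9, between 0 and 0.33 points in absolute size, and gives it an item in common with Depression/Self Perception. How much correlation the shared item adds depends on inter-item correlations that the documents do not give, so no figure is put on it. The 1 to 5 range is wrong for all four scales: the upper limit is 4 for three of them and 4.43 for Scale 3.

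This rests on reading Q21 and Q31 as Q2l and Q3l, on lettering the rows in printed order to identify the two statements, and on all nine Coping items being answered. That Q3c is the intended item is an inference from the counts and the content. It would go too far to say that the scale scores in general come out wrong, or that a named outcome of the study is affected.

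**What to change.** Check the key against the source instrument (reference 37). If the slip is confirmed, replace Q3d with Q3c in Scale 2 and leave Q3d in Scale 3. Any Coping scores already computed should be recalculated from the item-level answers. Section 10.4 provides for completed questionnaires to be stored, so this should need no new data.

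Replace the stated range with 1 to 4 for Scales 1, 2 and 4, and 1 to 4.43 for Scale 3.

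As a minor clarification, state that the divisor is the number of items answered, and say whether a minimum number of answers is needed for a scale to be scored; the minimum is for the investigators to choose.

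The cost is a few lines in one appendix and, if scoring has begun, a rerun of one scale.
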